5.3.4 Early Discontinuation from the Study Treatment or Study

The criteria for enrollment and randomization are to be followed explicitly. If it is noted that a patient who does not meet the inclusion and exclusion criteria is inadvertently randomized and dosed, the [Medical Monitor](#) at Sponsor's designated CRO (Quintiles) and the Sponsor's [Medical Director](#) must be contacted immediately for discussion on how to proceed with the patient. The patient should be discontinued from the study if there is any compelling safety concern for the patient to continue. The various scenarios that may occur leading to discontinuation of the patient from study and/or treatment is detailed in [Table 2](#).

Table 2 Potential Scenarios for Early Discontinuation from Study and Treatment

Scenario	Discontinuation from Study Treatment	Discontinuation from Study	Replacement if necessary
Safety Concern during Treatment period: In case of a safety concern during Treatment period , Medical Monitor should be consulted and the safety and efficacy assessments per Follow-up period of Table 1 (Visit 9 to Visit 16) must be completed wherever possible.	Discontinue patient from Study Treatment.	Patient does not need to be discontinued from the study depending on the severity and nature of safety event but discontinuation from the study needs to be discussed with the Medical Monitor and/or Sponsor's Medical Director . Wherever possible and appropriate/safe, the patient should continue the schedule of assessments for the Follow-up Period of Table 1 (Visit 9 to Visit 16).	Patients will be analyzed as part of Safety and Efficacy analysis and such a patient will not be replaced.
Safety Concern after Treatment period: In case of a safety concern after Treatment period , the safety and efficacy assessments per Follow-up period of Table 1 (Visit 9 to Visit 16) must be completed where possible and Medical Monitor should be consulted.	Not Applicable.	Patient does not need to be discontinued from the study depending on the severity and nature of safety event but discontinuation from the study needs to be discussed with the Medical Monitor and/or Sponsor's Medical Director . Wherever possible and appropriate/safe, the patient should continue the schedule of assessments in the Follow-up Period of Table 1 (Visit 9 to Visit 16).	Patients will be analyzed as part of Safety and Efficacy analysis and such a patient will not be replaced.

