10.4.1 Primary Endpoint Analyses

10.4.1.1 Adverse Events

Treatment-emergent AEs are defined as AEs that first occurred or worsened in severity after the first administration of the IMP.

Summaries over SOC, PT and listings of AEs leading to death, SAEs, AEs, and AEs that led to discontinuation of study treatment will be presented. Summaries will also be presented by relationship to IMP and severity of the AE.

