16.1. ADVERSE EVENTS

Adverse Events (AEs) will be coded using MedDRA central coding dictionary, Version 19.1.

Treatment-emergent AEs are defined as AEs that first occurred or worsened in severity after the first administration of the IMP. Any AEs started after the informed consent form has been signed and before the first administration of the IMP will be considered as Non-TEAEs.

The relationship to study drug will be summarized as related and unrelated. AEs that are recorded as 'related', 'possibly' or 'probable' in the eCRF are categorized as 'related' whereas the AEs that are recorded as 'unrelated' and 'unlikely' are categorized as 'unrelated'. Missing relationship/missing severity would be considered by the worst case as "Related" and "Grade 5" respectively.

Listings will include TEAEs and Non-TEAEs. Separate listing will be provided for AEs leading to discontinuation, serious adverse events (SAEs) and deaths.

For each treatment group, TEAEs, non-TEAEs, drug related AEs, relationship to study drug, AEs leading to discontinuation and SAEs will be summarized by primary SOC and PT. Also, summary of National Cancer Institute Common Terminology Criteria for Adverse Events (NCI-CTCAE, version 4.03) will be presented by primary SOC and PT. AE tables include number and percentage of subjects and number of events.

An overall summary of adverse events will be produced including frequency counts of:

- number of subjects with at least one TEAE
- number of subjects with at least one non-TEAE
- number of subjects with at least one serious TEAE
- number of subjects withdrawn from treatment with at least one serious TEAE

Document:

CCI

Author:

PPD

Version Number:

1.0

Version Date:

06 Oct 2017

Template No: CCI

Reference: CCI

Effective Date: 01Apr2016

Copyright © 2009, 2010, 2012, 2016 Quintiles Transnational Corp. All rights reserved.

The contents of this document are confidential and proprietary to Quintiles Transnational Corp. Unauthorized use, disclosure or reproduction is strictly prohibited.

- number of subjects with at least one related serious TEAE
- number of subjects who discontinue from the study due to a TEAE
- number of subjects with at least one TEAE with CTCAE severity grade ≥ 3
- number of subjects with at least one related TEAE
- number of deaths

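### The overall adverse-event summary in SAP 16.1 has no row for a patient who stops IMP over a non-serious TEAE, has no serious TEAE and stays in the study

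*SAP*

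**What the plan says.** SAP 16.1 introduces its headline safety table with "An overall summary of adverse events will be produced including frequency counts of" and a list of rows. Two of them concern discontinuation:

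- "number of subjects withdrawn from treatment with at least one serious TEAE"
- "number of subjects who discontinue from the study due to a TEAE"

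The same section plans a table in which "AEs leading to discontinuation and SAEs will be summarized by primary SOC and PT", and a separate listing of such events. Neither is limited to serious events, and neither says whether IMP or the study is being discontinued.

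The protocol keeps the two kinds of discontinuation apart. For a safety concern during the treatment period, Table 2 in section 5.3.4 gives the instruction "Discontinue patient from Study Treatment", but on study participation it says "Patient does not need to be discontinued from the study depending on the severity and nature of safety event". It adds: "Wherever possible and appropriate/safe, the patient should continue the schedule of assessments for the Follow-up Period". For adverse-event reporting, Protocol 10.4.1.1 says that summaries and listings of "AEs that led to discontinuation of study treatment will be presented", with no seriousness condition.

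SAP 9 tabulates how many subjects discontinued treatment and the primary reason. SAP 14 summarises completed infusions and lists interruptions and premature stops.

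**The concern.** Safety and tolerability is the only primary objective, and stopping IMP because of an adverse event is a direct sign of poor tolerability. The overall summary is the table most readers will look at first. As specified, it has a treatment row tied to serious TEAEs and a study row tied to any TEAE, but none for stopping treatment because of any TEAE. The patients it passes over are those for whom a site does what Table 2 prefers: stop the infusions, keep the patient in the study and go on assessing.

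The treatment row has a second weakness. It links the stop to a serious TEAE with the word *with*, not *due to*. Presence of a serious event is enough; causation is not required.

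The narrowing is not declared. SAP 3.3, which records changes from the protocol's analysis, mentions only the mixed model.

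**Working it through.** The plan gives no figure to reproduce. The check is a classification of patient types against the two rows as worded, compared with the quantity in Protocol 10.4.1.1, namely discontinuation of study treatment because of an AE. That quantity is restricted here to TEAEs, as in the summary.

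| Patient | Treatment row (serious TEAE present) | Study row (due to a TEAE) | IMP stopped because of a TEAE |
|---|---|---|---|
| A. Stops IMP over a non-serious TEAE, no serious TEAE, stays in study | no | no | **yes** |
| B. Stops IMP over a non-serious TEAE, also has a separate serious TEAE, stays | yes | no | yes |
| C. Stops IMP voluntarily, has an unrelated serious TEAE, stays | yes | no | **no** |
| D. Stops IMP because of a serious TEAE, stays | yes | no | yes |
| E. Stops IMP and leaves the study over a non-serious TEAE, no serious TEAE | no | yes | yes |
| F. Receives all infusions, leaves the study in follow-up because of a TEAE | no | yes | no |
| G. Stops IMP and leaves the study because of a serious TEAE | yes | yes | yes |

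Reading down the columns:

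- Treatment row = B + C + D + G.
- Study row = E + F + G.
- Quantity wanted = A + B + D + E + G.

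The treatment row therefore omits A and E and includes C. Combining the two rows patient by patient gives B + C + D + E + F + G, which still omits A and brings in C and F. The wanted count cannot be recovered from the two rows.

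Type B matters for stating the gap exactly. Because the row says *with*, a patient who stops over a non-serious event but has any serious TEAE is counted. Within the summary, the patient counted nowhere as a discontinuation is type A only.

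For scale, SAP 7.2 gives 12 subjects planned per group, so one type A patient is 1/12 = 8.3% of an arm. The documents give no expected number of such patients.

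**The case against.** The strongest answer is that the output the protocol asks for is already planned. Protocol 10.4.1.1 calls for summaries over SOC and PT and for listings; it does not call for a row in an overall table. SAP 16.1 plans a SOC/PT table, by treatment group and with numbers of subjects, and a listing of AEs leading to discontinuation, neither limited to serious events. The SAP is written with reference to the protocol and declares no change to AE reporting, so its natural meaning is discontinuation of study treatment. SAP 9 and SAP 14 would also show the stopped infusions. With about 24 patients, all listed individually, a stop is unlikely to go unseen. The row list is open-ended, and the mock shells, which are not among the documents, may contain a further row.

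Most of this stands, and it sets the size of the point. A reader might infer that these patients disappear from the safety report, or that the treatment row misses every stop for a non-serious event. The documents support neither: the other outputs can show the patient, and type B is counted.

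Three things remain. The SOC/PT table and listing cover the patient with certainty only once *discontinuation* is defined, and the one headline row that attributes discontinuation to a TEAE concerns the study. The disposition reason in SAP 9 is not tied to an AE term, grade or relationship. And an open-ended list does not mend a row whose stated definition is too narrow in one direction and too wide in the other.

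It is also fair to say that Table 2 does not make staying in the study automatic. It depends on the nature and severity of the event, on discussion with the Medical Monitor and/or the sponsor's Medical Director, and on what is possible and safe.

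**Conclusion.** The point holds, and it is minor. As specified, the two discontinuation rows do not count a patient who stops IMP over a non-serious TEAE, has no serious TEAE and remains in the study. The treatment row can also count a stop that no adverse event caused. The defect is confined to the headline safety table and to one undefined term in the supporting table and listing.

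A reader might go further and infer that the summary would hide a substantial tolerability problem. The documents give no basis for that: they state no expected rate of stopping IMP, and disposition, exposure and, on the natural reading, the SOC/PT outputs would show it. The conclusion rests on the row wording taken literally and on the shells not adding a row that the SAP does not mention.

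**What to change.** In SAP 16.1:

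- Replace the treatment-withdrawal row with *subjects who discontinued IMP because of a TEAE*, and show beneath it *of which because of a serious TEAE*. Derive both from the action-taken item recorded for each AE (Protocol 8.1.1 and 8.1.1.1).
- Keep the study-discontinuation row as a separate row.
- In the SOC/PT table and the listing, present AEs leading to discontinuation of IMP, as Protocol 10.4.1.1 requires, and AEs leading to discontinuation from the study as two separately labelled categories.

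The last item should not be shortened to IMP only. In the 8-week follow-up Table 2 marks treatment discontinuation as not applicable, so an IMP-only definition would drop AEs that cause a patient to leave the study in that period and would leave only a count in the summary.

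The cost is SAP and shell wording and a little programming. No new type of data is needed, provided the action-taken responses identify discontinuation of IMP; the eCRF options are not shown, so this should be confirmed. No clinical rule changes.

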16.2. SUICIDALITY ASSESSMENT

A separate listing for suicidality assessment will also be presented.

16.3. LABORATORY EVALUATIONS

Results from both the central and local laboratory will be included in the reporting. Central laboratory results will be reported for hematology, clinical chemistry and urinalysis. A list of laboratory assessments to be included in the outputs is given in the protocol.

A summary will be provided for the incidence of abnormal values according to normal range criteria for the laboratory data. A listing of subjects with values outside the normal range in question will be presented. Urinalysis quantitative results will be summarized with descriptive statistics and qualitative results will be presented with frequency and percentages. All the results will be listed as well.

All parameters will be summarized descriptively and shift tables will be presented for categorical data. Hematology, Clinical Chemistry, Urinalysis and other tests with numeric data will be presented graphically.

16.4. ECG EVALUATIONS

The following ECG parameters will be summarized descriptively:

- Heart Rate (bpm)
- PR Interval (msec)
- QRS Interval (msec)
- QT Interval (msec)
- QTcF Interval (msec)

The overall assessment of the ECG (Investigator's judgment) will be summarized with frequency and percentage for the following categories:

- o Normal
- o Abnormal, Not Clinically Significant (ANCS)
- o Abnormal, Clinically Significant (ACS)

Document:

CCI

Author:

PPD

Version Number:

1.0

Version Date:

06 Oct 2017

Template No: CCI

Reference: CCI

Effective Date: 01Apr2016

Copyright © 2009, 2010, 2012, 2016 Quintiles Transnational Corp. All rights reserved.

The contents of this document are confidential and proprietary to Quintiles Transnational Corp. Unauthorized use, disclosure or reproduction is strictly prohibited.

Absolute values for QT and QTcF intervals will be classified as:

- ≥ 450 msec
- ≥ 480 msec
- ≥ 500 msec

Change from Baseline for QT and QTcF intervals will be classified as:

- > 30 msec
- > 60 msec

A listing for all ECG parameters will also be presented.

16.5. VITAL SIGNS

The following Vital Signs measurements will be summarized descriptively:

- Systolic Blood Pressure (mmHg)
- Diastolic Blood Pressure (mmHg)
- Heart Rate (bpm)
- Oral Body Temperature ($^{\circ}$ C)
- Weight (kg)

Listings will be provided for above vital signs parameters.

16.6. PHYSICAL EXAMINATION

The frequency (percentage) table for physical examinations along with a shift table of clinically significant findings will be summarized by body system. All the collected data will be listed as well.

17. PHARMACOKINETIC ANALYSIS

All PK analysis will be performed using PK Analysis Set.

17.1. PHARMACOKINETIC CONCENTRATIONS

A listing of PK blood sample collection times as well as derived sampling time deviations will be provided.

A subject listing of all concentration-time data will be presented. Individual subject concentration-time data will be graphically presented on linear and semi-logarithmic scales.

Document:

CCI

Author:

PPD

Version Number:

1.0

Version Date:

06 Oct 2017

Template No: CCI

Effective Date: 01Apr2016

Reference: CCI

Copyright © 2009, 2010, 2012, 2016 Quintiles Transnational Corp. All rights reserved.

The contents of this document are confidential and proprietary to Quintiles Transnational Corp. Unauthorized use, disclosure or reproduction is strictly prohibited.

Plasma concentrations of ARGX-113 will be summarized by nominal time point using the following statistics:

- Number of observations (n)
- Number of observations \geq lower limit of quantification (LLOQ)
- Arithmetic mean
- SD
- Geometric mean
- Geometric SD
- Minimum
- Median
- Maximum

If warranted by the data, concentrations may be further summarized by ADA presence. Concentrations of ARGX-113 that are below the limit of quantification (BLQ) will be set to the lower limit of quantification (LLOQ) for the computation of descriptive statistics. A figure of geometric mean concentration-time (in days) data (\pm SD, as appropriate; from the start of the first infusion) will be presented on linear and semi-logarithmic scales.

17.2. PHARMACOKINETIC PARAMETERS

For PK parameter calculations, Visit 1 pre-dose samples that are BLQ or missing will be assigned a numerical value of zero. Any anomalous concentration values observed at pre-dose on Visit 1 will be identified in the study report and used for the computation of PK parameters. Pharmacokinetic parameters will be computed if the pre-dose anomalous concentration is not greater than 5% of the observed maximum concentration (C_{max}). If a pre-dose concentration value on Visit 1 is greater than 5% of C_{max} in the profile, PK parameters for the profile shall not be included in the summaries but will be calculated and listed. Additionally, these anomalous pre-dose concentrations will be flagged in the concentration listings, with different symbols for those greater than or less than 5% of C_{max} .

Following C_{max} , BLQ values embedded between 2 quantifiable data points will be treated as missing when calculating PK parameters for Visit 7. If a BLQ value occurs at the end of the collection interval (after the last quantifiable concentration), it will be set to zero. If consecutive BLQ concentrations are followed by quantifiable concentrations in the terminal portion of the concentration curve on Visit 7, these quantified values will be excluded from the PK analysis by setting them to missing, unless otherwise warranted by the concentration-time profile.

The following PK parameters will be estimated for ARGX-113 by non-compartmental methods using actual elapsed time from start of dosing after Visits 1, 3, 5 and 7:

C_{max} maximum observed plasma concentration. If the end of infusion sample is collected more than one hour post infusion, C_{max} will be listed only and not included in summaries.

t_{max} the time of occurrence of C_{max}

Document: CCI
Author: PPD
Version Number: 1.0
Version Date: 06 Oct 2017
Template No: CCI
Effective Date: 01Apr2016
Reference: CCI

C_{trough}	plasma concentration observed at the end of the dosing interval at Visits 3, 5, 7, and 9. These concentrations will be included in summaries regardless of sampling time deviation.
$t_{1/2,\lambda_z}$	the apparent terminal half-life, calculated from $(\ln 2)/\lambda_z$ (Visit 7 only)
R_{ac}	accumulation ratio, calculated as $\text{Visit 7 } C_{\text{max}} / \text{Visit 1 } C_{\text{max}}$
AUC_{tau}	area under the concentration-time curve during the dosing interval. This parameter will be determined for each active subject and dose if there are two quantifiable postdose concentrations available. If the end of infusion sample is collected more than one hour post infusion, AUC_{tau} will be listed only and not included in summaries.
$AUC_{0-\text{infinity}}$	area under the concentration-time curve from time 0 (pre-infusion on Day 1 Visit 1) extrapolated to infinity over the entire course of therapy using time elapsed from the start of the first infusion. If the extrapolated area is greater than 20% of $AUC_{0-\text{infinity}}$, then $AUC_{0-\text{infinity}}$ will be listed but not summarized.

Subjects with partial data will be evaluated on a case-by-case basis to determine if sufficient data are available for reliable estimation of PK parameters.

The following summary statistics will be presented for all the PK parameters except for t_{max} :

- Geometric Mean
- Geometric Coefficient of Variation (GCV) % (calculated as $GCV = 100 * \sqrt{\exp(s^2) - 1}$, where 's' is the SD of the data on a log scale.
- Arithmetic mean
- SD
- Minimum
- Median
- Maximum
- Number of observations

For t_{max} the following summary statistics will be presented:

- Number of observations
- Median
- Minimum
- Maximum

If warranted by the data, PK parameters may be further summarized by ADA presence.

The following PK parameters will be calculated for Visit 7 for diagnostic purposes and listed, but will not be summarized.

$t_{1/2}$, Interval	The time interval (h) of the log-linear regression to determine λ_z .
$t_{1/2}$, N	Number of data points included in the log-linear regression analysis to determine λ_z .
Rsq	Coefficient of determination for calculation of λ_z (Regression coefficient). If Rsq < 0.800, then λ_z and related parameters will be listed but not included in summary statistics.

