- f. Sampling for clinical laboratory tests is to be performed pre-dose on dosing days and tests will include hematology (hemoglobin, platelet count, white blood cell count with differential); blood chemistry (including creatinine, creatinine clearance, blood urea nitrogen [BUN], glucose, alanine aminotransferase [ALT], aspartate aminotransferase [AST], total bilirubin, gamma-glutamyl transferase [GGT], C-reactive protein [CRP], alkaline phosphatase [AP], lactate dehydrogenase [LDH], uric acid, albumin, potassium, calcium, sodium, thyroglobulin, International normalized ratio or activated partial thromboplastin time [aPTT], CD19 counts). Patients need to be fasting for at least 8 hours prior to this sampling.
- g. Sampling for pharmacodynamic biomarkers is to be performed pre-dose on dosing days and include anti-AChR antibodies and immunoglobulin G and its sub-types. Analysis of anti-AChR antibodies will include anti-AChR binding antibodies and anti-AChR blocking antibodies. IgG measurements include total IgG, IgG subtypes (IgG 1, IgG 2, IgG 3, and IgG 4). In addition, IgA, IgD, IgE, and IgM will also be assessed.
- h. ECG (heart rate, PR, QT, and QRS interval) will be read locally and should be performed pre-dose on dosing days.
- i. Pharmacokinetic (PK) assessments should be done both pre- and post-dose (within 30 minutes prior to start of infusion for pre-dose sample and within 30 minutes after end of infusion for post-dose sample) on all IMP infusion days.
- j. Serum pregnancy test must be performed in women of childbearing potential at Screening from the blood sample collected for clinical laboratory tests at the central laboratory.
- k. Urine pregnancy test will be performed locally pre-dose at Visits 1, 3, 5, 7, 11, and 16/EoS/ED.
- l. Tests to assess HbsAg, anti-HCV antibodies, Follicle stimulating hormone (FSH), HIV antibodies and tuberculosis serology (QuantiFERON®-TB Gold) test will be performed at the central laboratory.

argenx
ARGX-113-1602, Version 2.0
ARGX-113

- m. A blood sample for the optional pharmacogenetic testing is to be collected before the first dose of the Investigational Medicinal Product is administered at Visit 1 (Baseline) after a separate pharmacogenetic ICF has been signed, and will be stored for pharmacogenetic analysis. Only if the blood sample at Visit 1 is missed, the sample should be drawn at Visit 3 before the administration of the Investigational Medicinal Product.

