7.12 Handling Missed Doses of the Investigational Medicinal Product

If the patient misses more than one dose of the IMP he/she may be replaced although may continue in the study and maybe evaluable for safety and efficacy evaluation, for details refer to [Table 2](#).

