8.3 Pharmacokinetics

In order to assess the PK parameters of ARGX-113, blood samples will be collected from each patient as presented in [Table 1](#). Concentrations will be determined using a validated assay. The actual date and time of collection of blood sample will be recorded in the relevant section of the eCRF.

Pharmacokinetic calculations will be performed by Quintiles using Quintiles SOPs and standard non-compartmental and/or compartmental methods, as appropriate.

The appropriate PK parameters will be calculated after single (Visit 1) and multiple administrations (Visits 3, 5, and 7) of ARGX-113 using individual concentration data in plasma and actual sampling times:

C_{\max}	maximum observed plasma concentration
t_{\max}	the time of occurrence of C_{\max}
C_{trough}	plasma concentration observed at pre-dose at Visits 3, 5, and 7
$t_{1/2,\lambda_z}$	the apparent terminal half-life, calculated from $(\ln 2)/\lambda_z$ (Visit 7 only)
R_{ac}	accumulation ratio, calculated as Visit 7 C_{\max} /Visit 1 C_{\max}

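### SAP 17.2 summarises Ctrough whatever its sampling time, so a nominal pre-dose sample drawn after that visit's infusion has started would be averaged as a trough

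*SAP*

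**What the plan says.** Protocol 8.3 defines Ctrough as the "plasma concentration observed at pre-dose at Visits 3, 5, and 7". SAP 17.2 widens this to the "plasma concentration observed at the end of the dosing interval at Visits 3, 5, 7, and 9" and then adds: "These concentrations will be included in summaries regardless of sampling time deviation".

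Protocol Table 1, footnote i, sets the PK sampling windows on infusion days: "within 30 minutes prior to start of infusion for pre-dose sample and within 30 minutes after end of infusion for post-dose sample".

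Two neighbouring parameters in SAP 17.2 carry a timing exclusion. For Cmax: "If the end of infusion sample is collected more than one hour post infusion, C_{max} will be listed only and not included in summaries". For AUCtau: "If the end of infusion sample is collected more than one hour post infusion, AUC_{tau} will be listed only and not included in summaries".

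SAP 17.1 separately summarises plasma concentrations by nominal time point and has no timing exclusion. SAP 6.5 applies no visit windowing.

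**The concern.** Visits 3, 5 and 7 are infusion visits. A sample labelled pre-dose but drawn once the infusion is running breaches the 30-minute pre-dose window, so it is a sampling-time deviation, and the SAP sentence keeps it. It no longer measures the end of the previous dosing interval. Visit 9 has no infusion and is not affected.

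Elsewhere SAP 17.2 lists unreliable values without summarising them. Besides the Cmax and AUCtau rule, it does so for profiles with a Visit 1 pre-dose value above 5% of Cmax, for AUC0-infinity with more than 20% extrapolated, and for terminal-phase parameters with Rsq below 0.800. Ctrough is the one parameter for which the section expressly sets timing aside.

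Ctrough is a named secondary endpoint, summarised in about 12 active patients. At that size a single contaminated value can visibly move a visit mean.

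**Working it through.** The plan states no figure on this point, so there is none to reproduce.

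**Inputs from the documents:** weekly dosing, 2-hour infusions, 12 patients planned per arm (SAP 7.2).

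**Assumptions:** one-compartment decline; half-life h of 3 to 6 days, which is not in the documents; one affected patient; the other 11 set equal to the true trough.

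**Step 1. Fraction left after 7 days.** r = 2^(-7/h). For h = 3, r = 0.198. For h = 6, r = 0.445.

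**Step 2. Sample drawn at the end of the infusion (worst draw time).** Near steady state its ratio to the true trough is about 1/r: 1/0.198 = 5.04 and 1/0.445 = 2.24.

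**Step 3. Effect on a mean of 12.**
- Arithmetic mean, (1/r - 1)/12: 4.04/12 = 34% (h = 3); 1.24/12 = 10% (h = 6).
- Geometric mean, (1/r)^(1/12) - 1: 5.04^(1/12) = 1.144, so 14%; 2.24^(1/12) = 1.070, so 7%.
- Median: unchanged here, since 11 of the 12 values are equal. With real spread, one value can move it by at most a step in rank.

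Step 2 is a steady-state approximation. At Visit 3 only one dose has been given and the ratio is 1 + 1/r. The arithmetic shift is then (1/r)/12: 5.04/12 = 42% (h = 3) and 2.24/12 = 19% (h = 6).

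**Step 4. Earlier draws and other half-lives.** A one-compartment calculation with the 2-hour infusion modelled explicitly gives, for Visit 7 (ratio to true trough; arithmetic / geometric mean shift with n = 12):

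| Half-life | 30 min after start | 60 min after start | End of infusion |
|---|---|---|---|
| 2 days | 3.53; +21% / +11% | 6.04; +42% / +16% | 11.00; +83% / +22% |
| 3 days | 2.00; +8% / +6% | 3.00; +17% / +10% | 4.97; +33% / +14% |
| 5 days | 1.43; +4% / +3% | 1.85; +7% / +5% | 2.70; +14% / +9% |
| 7 days | 1.28; +2% / +2% | 1.56; +5% / +4% | 2.13; +9% / +7% |

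**Step 5. Comparison with the error that the SAP does guard against.** An end-of-infusion sample one hour late lowers the concentration by 1 - 2^(-1/(24h)): 1.0% for h = 3 and 0.5% for h = 6. On this model, the timing error that triggers exclusion is far smaller than the one that is expressly kept.

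**The case against.** The best case for the plan is that keeping observed troughs and listing their timing is a deliberate, disclosed choice that avoids post hoc dropping in a small trial. Several safeguards also exist:

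- The PK Analysis Set (SAP 5) leaves out subjects with major deviations thought to affect PK.
- SAP 17.2 judges partial data case by case.
- SAP 17.1 lists collection times and deviations.
- Protocol 6.4 puts the pre-dose assessments before dosing, and protocol 9.3 calls for full source data verification.
- A sample drawn during the infusion arguably falls outside the definition of a trough, and a draw at the very end is unlikely given the separate post-dose sample.
- Protocol 10.4 plans no formal hypothesis testing.

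This limits the consequence but does not close the gap. The analysis-set exclusion needs a major deviation, has no stated criteria and removes the whole subject. The case-by-case rule concerns partial data. A listing does not correct a summary. The definition does not help when the next sentence tells the analyst to ignore sampling time.

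A reader might also infer more than the documents support:

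- **That the sentence forces troughs after a missed dose into the mean.** It speaks of sampling time, and a missed dose is a dosing deviation. Protocol 7.12 foresees that a patient who "misses more than one dose of the IMP he/she may be replaced although may continue in the study", but the SAP is silent on that patient's next trough. It does not order its inclusion.
- **That Cmax and AUCtau exclude mistimed samples in general.** Their only timing exclusion is an end-of-infusion sample more than one hour late. One drawn 30 to 60 minutes late breaches the protocol window and stays in, and AUCtau has no rule for a mistimed pre-dose sample.
- **That accumulation or exposure would be misread.** The accumulation ratio is prespecified as Visit 7 Cmax over Visit 1 Cmax, so a mistimed trough does not enter it. After a missed dose, exposure really is lower.
- **That ordinary variation within the plus or minus 1 day visit window is a fault of the same kind.** Such samples are still taken before the next infusion and should be kept.

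**Conclusion.** The point holds in a narrow form. As worded, SAP 17.2 averages a nominal pre-dose sample at Visit 3, 5 or 7 even when it was drawn after that visit's infusion began, and no existing safeguard reliably removes it. With an assumed half-life of 3 to 6 days, one such sample among 12 raises the arithmetic mean by about 34% to 10% and the geometric mean by about 14% to 7% if drawn at the end of the infusion near steady state. The shift is larger at Visit 3, smaller for earlier draws, and slight for the median. These sizes rest on the assumed half-life and on one affected patient. Nothing in the documents says how often this would happen. Because Ctrough is descriptive and individual times are listed, the change is worth making but minor. Missed doses are a separate omission that needs a clarifying line.

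**What to change.** Amend the Ctrough sentence in SAP 17.2 along these lines:

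> A Ctrough sample taken after the start of that visit's infusion is listed and flagged but not summarised. Values with any other sampling-time deviation, including variation within the plus or minus 1 day visit window, are retained.

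Apply the same exclusion to the pre-dose nominal-time summaries in SAP 17.1. Otherwise the value removed in 17.2 is still averaged there, and two summaries of the same samples disagree.

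As a secondary clarification, state that a trough not preceded by the scheduled dose is also listed and flagged but not summarised.

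The cost is a few lines in the SAP and an occasional value lost from one visit's summary. The patient's other PK data stay in, which would not be so if the PK Analysis Set exclusion were used for the purpose.
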